#### 10.2.2.1 Suspected gonorrhoea, chlamydia, or Pelvic infection

Clinicians diagnosing suspected gonorrhoea, chlamydia or pelvic infection on the basis of exam will postpone subject enrollment and prescribe appropriate treatment. In addition, treatment will be initiated and/or adjusted as appropriate based on laboratory results when available and include treatment of sexual partners when indicated. Once treatment is complete, the subject may return for continued screening and may be enrolled within a month of the start of screening if there is no obvious sign of infection per clinician judgement.

#### 10.2.3 Ultrasound examination

Ultrasound examinations pre or post-enrollment are not required and should not be standard. Clinician judgement should be used to determine whether, when, and what type of ultrasound examination is needed. Potential reasons include, but are not limited to:

- difficult insertion
- suspected perforation
- suspected expulsion
- pregnancy

Steps should be taken to ensure that the participant does not look at the ultrasound screen and that pictures are not shown to the subject to ensure subject blinding is maintained.

#### **10.2.4** Pap Test

A screening Pap test will be completed for subjects at screening if potential participant is not in compliance with normal standard of care guidelines regarding Pap testing. ACOG guidelines should be used for current Pap test standard of care requirements. Participants will need to provide results of previous Pap to confirm results are within ACOG Pap test standard of care requirements for Pap testing not completed by the site. Participant pap test results, as required per ACOG guidelines, are required prior to the participant being enrolled and randomized into the study. When scheduling Screening visits, sites should request subject bring Pap results with them to the Screening visit. If additional testing or treatment is required based on Pap results, this should be completed prior to enrollment.

# 10.2.5 Laboratory Assessments

Laboratory evaluations:

See Visit Procedures section 11.

# 10.2.5.1 STI screening

During screening visits, at the time of the pelvic exam, all participants will be screened for gonorrhoea and chlamydia using nucleic acid amplification testing of urine, vaginal, or endocervical swabs. Asymptomatic participants do not need to wait for gonorrhoea and chlamydia results to receive their assigned IUD.

For a few asymptomatic women, IUD insertion might occur before results of a positive gonorrhoea or chlamydia test are available. For these participants, treatment will commence as soon as possible once results of a positive test are received. IUDs should not be removed unless severe pelvic infection is suspected.

#### 10.2.5.2 Urine pregnancy testing

Participants will undergo urine pregnancy testing at screening and enrollment (if enrollment occurs on a separate day from screening). A negative test is required to proceed with possible IUD placement. In addition, urine pregnancy tests will be administered during follow-up visits. Each facility will use the test kits and specific laboratories normally used for routine services at the facility's local laboratory.

Note: if urine pregnancy test is positive at screening, no further action is required and subject will become a screen failure. If positive urine pregnancy test report is based on home pregnancy test result post enrollment, subject should be scheduled to come in for an Unscheduled visit to have quantitative blood pregnancy test performed. If confirmatory quantitative blood pregnancy test comes back negative, then subject will be allowed to stay in the study.

# 10.2.6 Specimen collection and Processing

Each site will establish standard operating procedures, including specimen chain of custody and quality control procedures, for all protocol-specified laboratory tests before study initiation as

per local laboratory requirements for sample processing in accordance with standards of good clinical and laboratory practice.

# 10.3 Subject Assessments

# 10.3.1 Follow Up Form

Administration of a follow-up form will occur at Visit 2, Visit 3, Visit 4, Call 1, Visit 5, Call 2, Visit 6, Call 3 and Exit for subjects to answer questions about the desire to continue use of the IUD, IUD acceptability, last menstrual cycle, vaginal bleeding, pelvic pain, and use of alternative contraception since the preceding visit.

# 10.3.2 Daily Diary

For the first 12 months of use, participants will maintain a daily diary to record bleeding/spotting. Each form will collect one cycle of information consisting of 28 days of daily records. The form will also be used to record the use of any additional contraceptives (e.g. condoms) and coitus within that full 28-day cycle. Site staff will review responses carefully to ensure there are no questions about responses provided by the subject. The information from the daily diaries will be entered in the corresponding CRFs. Each site will retain originals of the completed diaries as source documents and certified copies will be uploaded to the study document repository or EDC at Health Decisions.

# 10.3.3 Other Contraceptive Use

In the second and third years, participants will record cycle-to-cycle use of any other contraceptive methods. The forms will be used to capture information on other contraceptives used for the six month period between site visits. The information from the forms will be entered in the corresponding CRFs during Visit 6, and Exit. At Calls 2 and Call 3 the site will ask information relative to other contraceptives used since the previous visit in order to prompt subjects to continue completing the forms; however, when the forms are returned at the clinic visits the form responses will be the primary source which will be used for data entry rather than information discussed during the calls that sites may have recorded in the subject's source. Each site will retain originals of the completed forms as source documents and certified copies will be uploaded to the study document repository or EDC at Health Decisions.

# 10.3.4 Post Placement Pain Forms

During the enrollment visit, a Clinic Post Placement Pain Form will be completed by the subject to record her baseline pain measurement after speculum placement and then pain measurements immediately and ten minutes after IUD placement. During the Exit Visit, the subject will complete a measurement of pain immediately after IUD removal on the bottom of the Clinic Post Placement Pain Form.

A separate Home Post Placement Pain Form will be sent home so subjects can record their maximum daily pain for 6 days following IUD placement. Also on this form, the subject will provide information on satisfaction with the IUD and use of pain medications. This form will be turned in at the 6 week visit.

CCN016 Version #: 03.00 Version Date: 19Dec2018 Page 29 of 76

#### 11 EVALUATIONS BY VISIT

# 11.1 Screening and Enrollment/IUD Insertion

Visit 1 includes screening, enrollment, and IUD insertion. Screening and enrollment can occur on the same day provided the potential participant meets eligibility criteria at the time of screening, and is not at risk for luteal phase pregnancy based on history of unprotected intercourse within her current menstrual cycle. If the participant is at risk for pregnancy in the current cycle or is suspected to have gonorrhea, chlamydia, or pelvic infection, enrollment should be deferred. If the subject is under 21 years of age, no Pap is required per ACOG guidelines. If the potential participant is unable to provide results of previous Pap, defer enrollment until Pap results are available confirming treatment would not be required.

# 11.1.1 Screening Procedures

At the screening visit, study staff will conduct administrative and regulatory procedures (including obtaining written informed consent, providing contraceptive counselling, obtaining medical and reproductive health history, performing pelvic examinations, and collecting laboratory specimens for testing). Potential participants will provide written consent before any screening procedures are initiated. If needed, sites will refer women who are not eligible for the study for further care, if relevant services are not available at the research site or clinic. If a subject is a screen failure on her first study participation attempt, she may be rescreened one time per the Investigator's discretion.

**Table 02. Screening Visit Procedures** 

Component	Procedures
Administrative and Regulatory	
 
Obtain written informed consent, HIPAA Authorization and Assent (if applicable)
 
Assign Subject Identification number
 
Assess eligibility
 
Collect participant's contact information (e.g., cell phone, home phone, email, etc.). Note: If the subject has a cell phone, study staff should call the participant's cell phone number at least one time prior to enrollment to ensure number correctly connects to the subject.
 
File paper forms in a secure location
 
Provide reimbursement
 
Schedule next visit
 

Contraceptive Counselling	Describe contraceptive options, study IUDs, and answer potential participant questions
Clinical	
 
Collect demographic information
 
Obtain medical, gynecologic, menstrual, contraceptive, and reproductive history
 

CCN016 Version #: 03.00 Version Date: 19Dec2018 Page 30 of 76

	
 
Check vital signs and conduct pelvic examination
 
Collect concomitant medication information
 
Collect Pap test if subject is unable to provide results within ACOG standard of care guidelines
 

Laboratory Urine	Test urine for pregnancy
STI	Test endocervical or vaginal swabs or urine (per clinic testing standard) for Neisseria gonorrhoeae and Chlamydia trachomatis (GC/CT) to complete a Nucleic Acid Amplification Test (NAAT) (per clinic testing standard) and treat clinically suspected gonorrhoea, chlamydia, or pelvic infection per standard of care

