#### 7.4 Allowable Criteria

- has been using oral contraceptives, vaginal ring, or patch and is discontinuing the product to be enrolled
- has been using a contraceptive implant or IUD, but wishes to have the device removed prior to enrollment

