# 10.2.1 Medical, Demographic, and Reproductive Health History

At the screening visit, study staff will ask women about their medical and gynecologic history, including specific questions about any medical problems or current medications that may be contraindications to the use of any of the study methods. Women will also be asked about their past use of contraceptive methods as relevant and details about their previous pregnancies, if any. General subject demographic information (i.e. race, ethnicity, level of education, etc.) will also be collected at screening.

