# 11.1.2 Visit 1 (Enrollment Procedures and IUD Insertion)

Potential participants will usually proceed to enrollment procedures immediately after successful screening (i.e., screening and enrollment visits can occur on the same day).

The protocol allows same-day enrollment and IUD insertion in these potential participants:

- Women not using hormonal contraception who are in the first 7 days of the menstrual cycle,
- Women who have been correctly and consistently using a reliable hormonal method of contraception before screening (OCs, patch, ring, implants) once these methods are stopped/removed,
- Women who have been using any type of IUD (same-day removal and study enrollment is acceptable),
- Women who are ≥ 30 days post uncomplicated medical abortion who have been consistently using a reliable hormonal method of contraception before screening (OCs, patch, ring) or have not had vaginal intercourse since pregnancy termination,
- Women who are ≥ 30 days post first, second or third trimester surgical abortion who have been consistently using a reliable hormonal method of contraception before screening (OCs, patch, ring) or have not had vaginal intercourse since pregnancy termination,
- Non-breastfeeding women who are ≥ 30 days post-delivery who have been consistently using a reliable hormonal method of contraception before screening (OCs, patch, ring) or have not had vaginal intercourse since pregnancy termination.

CCN016 Version #: 03.00 Version Date: 19Dec2018 Page 31 of 76

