# 24 APPENDIX 1: SCHEDULE OF ASSESSMENTS

Study Procedures	Screening					Tr	eatment I	Period				Follow Up	Unscheduled
Visit Number	SCRN	V1	V2	V3	V4	C1	V5	C2	V6	С3	EXIT 	C4	UNS^
Treatment Period*	N/A	Day 1	6 Wks	3 Mos	6 Mos	9 Mos	12 Mos	18 Mos	24 Mos	30 Mos	37 Mos	17 Days	VAR
Informed consent, HIPAA Authorization, Assent (if applicable)	X												X
Assign Subject Number	X												
Obtain/Update Contact Information	X	X*	X	X	X	X	X	X	X	X	X		X
Determine Eligibility (Inclusion/ Exclusion)	X	X*											
Contraceptive Counselling	X										X		X
Demographics	X												
Medical, contraceptive, gynecological, menstrual, reproductive history	X	X*											
Vital signs 	X	X*											X
Pelvic exam 	X 	X*											X
Assess (and treat as applicable) for STIs/RTIs	X	X*	X	X	X		X		X		X		X
Pregnancy test (urine) 	X	X*	X	X	X		X		X		X	X	X
Endocervical, vaginal or urine specimen collection for GC/CT NAAT 	X	X*											X
Randomize subject		X											
Provide reimbursement	X	X	X	X	X		X		X		X		X
Schedule next visit	X	X	X	X	$X^3$	X	$X^3$	X	$X^3$	X	$X^6$		X
Insert IUD		X											
Assess ease of insertion		X											
Collect subject insertion pain level 		X											
Dispense Home Post Placement Pain Form		X											
Collect Home Post Placement Pain Form			X										
Collect IUD continuation/removal information 			X	X	X	X	X	X	X	X	X		X
Collect previous menstrual cycle, bleeding, pain information 			X	X	X	X	X	X	X	X	X		X
Ask IUD Acceptability Questions 			X	X	X	X	X	X	X	X	X		X
Confirm IUD placement 			X	X	X	X	X	X	X	X	X		X
Inquire on desire for continued IUD use 											X		X

CCN016 Version #: 03.00 Version Date: 19Dec2018 Page 61 of 76

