7.2. Analysis of Baseline Data

Baseline variables will be summarized for the ITT, User, Per Protocol and Efficacy Analysis populations, and for the Treated and Lost to Follow-Up Populations under the condition stated in Section 5. The following baseline measures collected at the screening and enrolment visits will be summarized by treatment group:

- Demographic data: age, ethnicity, race, parity, marital status, level of education
- Vital signs
- Substance use: tobacco use, alcohol use, marijuana use and illicit drug use
- Medical history including prior and concomitant medications
- Gynecological history

- Infection history (Pre-treatment signs and symptoms of: (urinary tract infection, yeast infection, bacterial vaginosis, pelvic infection, Endometriosis, and STIs)
- Contraceptive history
- Pregnancy history

Data will be presented in summary tables by treatment group, site and overall. Categorical variables, and continuous variables that have been categorized at discrete levels, will be summarized by frequencies and percentages. Continuous variables will be summarized by means, standard deviations, medians, interquartile ranges, minima and maxima.

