7.5.2 Statistical methods

The descriptive statistics of per-subject mean and median number of evaluable cycles and the proportion of evaluable cycles that include any heavy bleeding, a prolonged bleeding episode (e.g., greater than 14 days), amenorrhea (absence of all bleeding and spotting), or bleeding in more than 1/3 of days in the evaluable cycle will be tabulated. In addition, descriptive statistics of bleeding diary data as described by Mishell, et al (2007) such as the mean, median, and range of the total number of heavy, moderate, light bleeding, or spotting days per evaluable cycle will be reported without considering the feature of repeated cycles from same study participants.

To incorporate the nature of repeated measures and partial evaluable cycles, a multinomial regression with generalized estimating equation (GEE) approach will be used to estimate and compare the mean, and total number of heavy, moderate, light bleeding, or spotting days per 28-day cycle equivalent between treatment groups (Liang and Zeger, 1986, and Lipsitz et al., 1994).

Note that if 1) there are sizeable participants discontinued early (e.g., 20% of IUD removal) due to increased menstrual blood loss or due to intermenstrual bleeding/spotting, and 2) the proportions of these two reasons of discontinuation are notably different between treatment groups (P-value < 0.1), the analyses of observed bleeding diary data are likely to be biased due to informative censoring and attrition (Hubacher et al., 2009). In this event, subgroup supporting analyses based on participants' discontinuation reasons related and non-related to blood loss/bleeding/spotting will be conducted. A stratified bleeding diary supporting analysis based on the same blood loss/bleeding/spotting related reasons will also be performed to compare the results from the above analyses. The findings of these supportive analyses will be interpreted cautiously.

For the analysis of pelvic pain data, the proportions of participants experiencing any pelvic pain during 28-day cycle, pelvic pain during period, outside of period, and both during and outside of period will be calculated using binomial distribution for each group, and compared between groups using chi-square tests. In addition, generalized linear models with GEE for repeated pelvic pain outcomes will be used to further explore the differences in frequencies of pelvic pain between study groups.

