7.6.7 Characteristics of last menstrual period and product satisfaction

Acceptability data from the User Population on the last menstrual cycle and product satisfaction overall are derived from subject bleeding and satisfaction questionnaires and participant interviews conducted during the six clinic visits and during the three phone calls over the study period.

Data on bleeding and pelvic pain include number of days of bleeding, volume of blood loss (light, medium, heavy), acceptability of blood loss, level of cramping, and intermenstrual bleeding/spotting/cramping. Summaries will be described in contingency tables and displayed graphically in bar charts, by study visit and overall. Chi-squared tests for binary and ordinal outcome data (e.g., light, moderate, heavy blood loss) will be used to compare treatment groups at each visit/phone call. Generalized linear models with GEE will be used to compare the two treatment groups on these measures over time.

As noted in the previous section, if evidence of informative censoring exists due to participants' discontinuation reasons related to bleeding or pain, similar subgroup and stratified supporting analyses will be used to evaluate the impact of censoring mechanism on the results of the bleeding and pain safety data analysis.

Product satisfaction includes three measures: level of satisfaction with the study IUD, whether the participant would recommend the study IUD to others, and how the product compared to expectations. Each measure will be summarized in frequency and percentage by visit and site. A generalized linear model will be used to evaluate the time trend of product satisfaction between groups and to compare the means of changes of satisfaction between groups across all post insertion time points.

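### The GEE comparisons of bleeding and pelvic pain name no baseline covariate, so they give up whatever precision parity and screening history could add

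*Protocol*

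**What the plan says.** **What is collected before randomisation.** Protocol Table 02 (screening) lists "Obtain medical, gynecologic, menstrual, contraceptive, and reproductive history". The schedule in Appendix 1 has the matching row, "Medical, contraceptive, gynecological, menstrual, reproductive history", marked at screening and again at Visit 1 when enrollment falls on a separate day. Protocol 10.2.1 adds: "Women will also be asked about their past use of contraceptive methods as relevant and details about their previous pregnancies, if any". Protocol 9.1 stratifies randomisation by parity.

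**Who may enter.** Protocol 7.4 admits a woman who "has been using oral contraceptives, vaginal ring, or patch and is discontinuing the product to be enrolled", and also women leaving an implant or another IUD. Protocol 11.1.2 allows a previous IUD to be removed and the study IUD inserted on the same day.

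**How the baseline data are used.** SAP 7.2 is descriptive: "The following baseline measures collected at the screening and enrolment visits will be summarized by treatment group". For diary bleeding, SAP 7.5.2 says that "a multinomial regression with generalized estimating equation (GEE) approach will be used to estimate and compare the mean, and total number of heavy" and lighter bleeding days between groups. Diary pelvic pain is compared by chi-square tests and then GEE. For last-period bleeding and pain, SAP 7.6.7 (the section on the last menstrual period and satisfaction) gives chi-squared tests at each visit or call, and then: "Generalized linear models with GEE will be used to compare the two treatment groups on these measures over time". No baseline covariate is named in any of these.

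**Where adjustment does appear.** SAP 7.4.2 treats parity and earlier contraceptive use, with hormonal methods as the example, as suspected prognostic factors. This is only in the supporting Cox model for discontinuation, and only for factors that pass a 0.10 significance screen.

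**The concern.** Bleeding patterns and pelvic pain with dysmenorrhea are named secondary objectives, and they carry the rationale for a smaller device. Protocol section 1 says that nulliparous women typically have more side effects than parous women. Women coming off a pill, an implant or a copper IUD may also differ in how they bleed, whichever study device they receive. If so, part of the between-woman variation could be explained by data already in hand. With 4:1 allocation the control arm of about 220 women limits precision, so unexplained variation there is costly. At stake is the width of the intervals and the power of these comparisons, not their validity.

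**Working it through.** **The plan's own figure.** No SD, interval width or power is given for bleeding or pain. The only power figure for a device comparison is about 87% for 12-month continuation (Protocol 19.1: 70% on control, a 10-point gain, 800 v 200 women, up to 5% lost). It can be reproduced:

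- Women after 5% loss: 190 and 760. Events: 190 × 0.30 + 760 × 0.20 = 57 + 152 = 209.
- Hazard ratio: ln 0.8 / ln 0.7 = 0.626.
- Freedman's formula with 4:1 allocation: z = (1 − 0.626) × √(209 × 4) / (1 + 4 × 0.626) = 3.09.
- Power: Φ(3.09 − 1.96) = 87.1%.

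The point below does not depend on this figure.

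**Difference in per-woman means.** The inputs are 880 v 220 women (Protocol 4.1), two-sided 95% intervals (SAP section 6), and a correlation r between the baseline variables and a woman's mean outcome. The correlation is assumed, because the documents give none.

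- Unadjusted half-width: 1.96 × SD × √(1/220 + 1/880) = 0.148 SD.
- Adjusted half-width: 0.148 SD × √(1 − r²).
- Equivalent sample size: 1 / (1 − r²).

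| r (assumed) | half-width (SD) | narrower by | equivalent sample |
|---|---|---|---|
| 0 | 0.148 | 0% | ×1.00 |
| 0.2 | 0.145 | 2.0% | ×1.04 |
| 0.3 | 0.141 | 4.6% | ×1.10 |
| 0.4 | 0.135 | 8.3% | ×1.19 |
| 0.5 | 0.128 | 13.4% | ×1.33 |

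The SAP still states 800 v 200. The unadjusted half-width is then 0.155 SD, and the percentages are the same.

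**Binary outcome.** The √(1 − r²) rule does not carry over to a logit link, so a simulation was run with one binary pain outcome per woman. It used 880 v 220 women, control log-odds of 0.2 at the covariate mean, a conditional device log odds ratio of −0.45, a standard normal covariate and 1,500 replicates. All of these except the arm sizes are assumptions.

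| covariate effect (log-odds per SD) | SD of risk difference: unadjusted → standardised | SE of log odds ratio: unadjusted → conditional | power |
|---|---|---|---|
| 0.5 | 0.0376 → 0.0368 (−2%) | 0.1518 → 0.1565 | 80% → 81% |
| 1.0 | 0.0372 → 0.0337 (−9%) | 0.1516 → 0.1672 | 70% → 79% |
| 1.5 | 0.0390 → 0.0323 (−17%) | 0.1515 → 0.1808 | 54% → 72% |

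The standardised risk difference becomes more precise. The conditional odds-ratio interval becomes wider on the log scale. Power still rises, because the conditional effect moves away from zero by more than its standard error grows.

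**The case against.** The strongest reply is that the gain is of unknown size and may be small. This stands. The documents give no correlation and no share of women switching from each method. Eligibility already narrows the range: Protocol 7.2 requires regular cycles of 21 to 35 days varying by no more than 5 days, though it does not limit flow or period pain. The diary runs for 12 months, so an effect of the earlier method confined to the first cycles would be diluted in a per-woman mean. SAP 7.4.2 suspects earlier method use of predicting discontinuation, which is only indirect support for bleeding or pain. One visit item in Protocol 19.2.2 is scored relative to normal, which partly builds in a woman's own baseline. These are also secondary comparisons with no stated power.

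Three stronger readings are tempting, and the documents do not support them:

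- *That the unadjusted comparison is biased, or leaves chance imbalance as an error.* Randomisation protects it at baseline, and ordinary standard errors already allow for chance imbalance. The bias risk that the SAP does identify, informative discontinuation, is addressed separately in 7.5.2 and 7.6.7.
- *That a definite gain, or a rise from some stated power, is being lost.* No power is stated for these endpoints, and the gain is nil if the variables are not prognostic. The chi-square comparisons yield tests, so any loss there is in power and not in interval width.
- *That usual flow, bleeding length and period pain are available for adjustment.* The documents say that a menstrual history is taken, but they do not show its items. The only menstrual feature they specify is cycle length and regularity.

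None of this weakens the case for parity, which is known for every randomised woman and which the protocol itself links to side-effect rates.

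**Conclusion.** The omission is confirmed in both documents. It costs efficiency only. For mean differences the loss runs from nothing (r = 0) through about 5% of interval width (r = 0.3) to about 13% (r = 0.5), and these correlations are assumed. For binary or ordinal outcomes a comparable gain exists only on a marginal scale, such as a risk difference, so the choice of reported quantity is part of the point. Adjustment is worth adopting because parity needs no new data and the earlier method should already be on file, since SAP 7.4.2 plans to use it. The form itself is not shown.

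**What to change.** In the GEE models of SAP 7.5.2 and 7.6.7 (bleeding and pain):

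- Pre-specify as fixed covariates, not screened by p-value, parity and the last contraceptive method before insertion (hormonal, copper IUD, other or none).
- Check the screening eCRF. Add menstrual items such as usual bleeding length, flow or period pain only if they are recorded there.
- Report the device difference standardised over the covariates, as a difference in mean days per 28-day cycle or a difference in risk, with robust standard errors that allow for repeated cycles within a woman.
- Keep the unadjusted tables and chi-square tests as planned.
- Settle the list before these device comparisons are run.

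The cost is a short SAP paragraph, one look at the eCRF and some programming. No new data are needed for the two core covariates, provided the eCRF holds the last method as expected. The SAP already foresees a later version with table shells, and it still cites protocol version 2.0 and 1000 women against about 1100 in protocol version 3.00, so the change can go into a revision that is due anyway.
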